5.5 Tumor Evaluation Visits

For patients in Arm A, an MRI will be performed within 48-72 hours of surgery and will be used as the baseline exam for the purposes of tumor response evaluation in the patients who undergo surgical resection.

In both study arms, disease status and tumor response will be assessed at eight-week intervals until objective disease progression, or as clinically indicated, beginning approximately 8 weeks following initiation of combination therapy with BBI608 and TMZ. Standard imaging studies will be performed according to institutional procedures. Tumor response will be evaluated using the guidelines for Response Assessment in Neuro-Oncology (RANO) Working Group criteria outlined in **Section 9**, and study Case Report Forms (CRFs) will include relevant lesion measurements as determined by the study site. De-identified radiologic image dictation report as well as de-identified copies of the radiologic images for independent review may be requested in cases where radiologic assessment is in question.

Once clinical or radiological progression of disease during BBI608 therapy is documented, patients may continue treatment with BBI608 at the discretion of their treating physician.

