Survival	Date of death due to any cause	Every 6 months thereafter**

*Passive follow-up only of radiologic imaging obtained subsequent to all on-study MRI scans and clinic visit notes detailing neurologic state and change in corticosteroid use.

**Alternative schedules of post-protocol therapy follow-up by study site may be discussed with the Sponsor.

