2. Stable non-enhancing (T2/FLAIR) lesions on same or lower dose of corticosteroids compared to baseline scan. IN the event that the corticosteroid dose was increased for new symptoms and signs without confirmation of disease progression on neuroimaging, and subsequent follow-up imaging shows that this increase in corticosteroids was required because of disease progression, the last scan considered to show stable disease will be the scan obtained when the corticosteroid use was equivalent to the baseline dose.
3. Patients must be stable clinically.#

Progressive Disease

Defined by ANY of the following:

1. Greater than 25% increase in the sum of the products of perpendicular diameters of enhancing lesions compared to the smallest tumor measurement obtained either at baseline (if no decrease) or best response, on stable or increasing doses of corticosteroids.**
2. Significant increase in T2/FLAIR non-enhancing lesion on stable or increasing doses of corticosteroids compared to baseline scan or best response following initiation of therapy,* not due to co-morbid events (e.g. radiation therapy, demyelination, ischemic injury, infection, seizures, post-operative changes, or other treatment effects).
3. Any new lesion.
4. Clear clinical deterioration not attributable to other causes apart from the tumor (e.g. seizures, medication side effects, complications of therapy, cerebrovascular events, infection, etc.) or changes in corticosteroid dose.#
5. Failure to return for evaluation due to death or deteriorating condition.
6. Unequivocal progression of non-measurable disease.

*Patients with non-measurable disease only cannot have a complete or partial response. The best response possible is stable disease.

**Stable doses of corticosteroids include patients not on corticosteroids.

#Clinical status will be assessed via ECOG Performance Score.

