For patients in Arm A during the run-in period with BBI608 monotherapy, the same DLT rules as for the combination therapy will apply. Enrollment will be held if ≥ 2 of 6 patients are unable to undergo resection due to DLTs. Enrollment will also be held if ≥ 2 of 6 patients have an unexpected surgical complication.

Initial enrollment will be to a 6-patient safety cohort in each arm. These patients will be evaluated for the occurrence of DLT during the first 28 days of combination treatment with BBI608 and TMZ. If DLT is observed in ≥ 2 of 6 patients evaluable for DLT, the initial dose of BBI608 for all patients in that arm will be reduced to the next lower dose level of 240mg twice daily, and an additional 6-patient safety cohort will be enrolled at that dose-level and evaluated for DLT as above. Enrollment will continue at a dose-level at which ≤ 1 of 6 patients experiences DLT. Dose modification is allowed according to the standard schedule for BBI608.

Cycles of therapy will consist of the patient taking BBI608 daily in combination therapy for 28 days. Tumor assessments will be performed every two cycles (eight weeks), or as otherwise clinically indicated.

The RP2D is defined as the dose level at which no more than one patient with DLT is observed among six patients. Once the RP2D has been reached for a given arm based on

DLT assessment rules outlined above, up to 24 additional evaluable patients may be enrolled at RP2D.

It is expected that up to 30 patients (including those enrolled to the DLT evaluation cohorts) will be enrolled in each arm.

Phase II

In both Phase Ib and Phase II, a study cycle will consist of 28 days of daily administration of BBI608 and TMZ administration on days 1-5 of each cycle. Pharmacokinetic (PK) and pharmacodynamic assessments will be performed in the first cycle only. Safety and tolerability of BBI608 in combination with TMZ will be assessed for the duration of the study treatment and for 30 days after the last dose of BBI608. Evaluation of anti-tumor activity of BBI608 in combination with TMZ will be performed at 8-week intervals while patients remain on study according to RANO.

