3.1.2. Phase II

Progression free survival (PFS) at 6 months of BBI608 administered in combination with TMZ: is defined as the proportion of patients who have survived without objective disease progression per RANO criteria for at least 6 months after enrollment.

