8.2.2.2. Progression Free Survival at 6 months (PFS-6, Phase 1 and Phase 2)

PFS data will be analyzed by arm. PFS summary in Arm B will be provided only when the number of patients in that arm is at least 10. The same rule applies to Arm A data.

Progression free survival at 6 months (PFS-6) is defined as the proportion of patients who have survived without objective disease progression per RANO criteria for at least 6 months after enrollment. The censoring rules for PFS will be detailed in 10.2. If a patient has not progressed or died at the time of analysis, PFS will be censored on the date of the last tumor assessment. This includes patients who are lost to follow-up or have withdrawn consent.

PFS in months is calculated as (first event date/censored date – date of first dose of any study drug + 1)/30.4375. Estimates of the PFS curves at 6 months will be obtained using the Kaplan-Meier method and will be presented along with the 80% CI using the normal approximation to the log transformed cumulative hazard rate.

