10. APPENDICES

10.1. Appendix 1.1 Further Definition of Endpoints

Table 2 Response Criteria

Evaluation of lesions	
Complete Response (CR):	
Requires ALL of the following:
 
 1. Complete disappearance of all enhancing measurable and non-measurable disease sustained for at least 4 weeks. 2. No new lesions. 3. Stable or improved non-enhancing (T2/FLAIR) lesions. 4. Patients must be off corticosteroids (or on physiologic replacement doses only). 5. Patients must be stable or improved clinically.[£]
Partial Response (PR):	
Requires ALL of the following:
 
 1. Greater than or equal to 50% decrease compared to baseline in the sum of products of perpendicular diameters of all measurable enhancing lesions sustained for at least 4 weeks. 2. No progression of non-measurable disease. 3. No new lesions. 4. Stable or improved non-enhancing (T2/FLAIR) lesions on same or lower dose of corticosteroids compared to baseline scan. 5. The corticosteroid dose at the time of the scan evaluation should be no greater than the dose at time of baseline scan. 6. Patients must be stable or improved clinically.[£]
Progressive Disease (PD):	
Defined by ANY of the following:
 
 1. Greater than 25% increase in the sum of the products of perpendicular diameters of enhancing lesions compared to the smallest tumor measurement obtained either at baseline (if no decrease) or best response, on stable or increasing doses of corticosteroids.** 2. Significant increase in T2/FLAIR non-enhancing lesion on stable or increasing doses of corticosteroids compared to baseline scan or best response following initiation of therapy,* not due to co-morbid events (e.g. radiation therapy, demyelination, ischemic injury, infection, seizures, post-operative changes, or other treatment effects). 3. Any new lesion. 4. Clear clinical deterioration not attributable to other causes apart from the tumor (e.g. seizures, medication side effects, complications of therapy, cerebrovascular events, infection, etc.) or changes in corticosteroid dose.[£] 5. Failure to return for evaluation due to death or deteriorating condition. 6. Unequivocal progression of non-measurable disease.

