10.2. Appendix 1.2 Censoring for Time to Event Data

Table 4 summarizes the censoring rules for the PFS analysis and displays censoring hierarchy for this study. Table 5 shows the general reasons for PFS censoring and where the censoring hierarchy in **Table 4** came from.

Table 4 Event or Censor Time for PFS and Censoring Hierarchy

Censoring Hierarchy	Situation	Date of Event or Censor	Event / Censor
1	No baseline radiological tumor assessment available	Date of First Dose	Censored
2	New anticancer treatment started and no tumor progression	Date of previous adequate radiological assessment immediately prior to start of new therapy or Date of first dose, whichever comes later	Censored
3	Tumor progression (per RANO) documented after 2 scan intervals following previous adequate radiological tumor assessment	Date of previous adequate radiological assessment or Date of first dose, whichever comes later	Censored
4, 5	No tumor progression (per RANO) and subject lost to follow-up or withdrawal of consent	Date of last adequate radiological Assessment or Date of first dose, whichever comes later	Censored
6	No post baseline radiological tumor assessment available and no death reported within 2 scan intervals following the date of the first dose of study drug (BBI608)	Date of First Dose	Censored
7	No post baseline radiological tumor assessment available but death reported within 2 scan intervals following the date of the first dose of study drug (BBI608)	Date of Death	Event

	No tumor progression (per RANO) and no death reported within 2 scan intervals following last adequate radiological tumor assessment	Date of last adequate radiological tumor assessment or Date of first dose, whichever comes later	Censored
	No tumor progression (per RANO) but death reported within 2 scan intervals following last adequate radiological tumor assessment	Date of death	Event
	Tumor progression (per RANO) documented within 2 scan intervals following previous adequate radiological tumor assessment	Earliest of the target, non-target and new tumor assessment dates	Event

Notes: (1) Symptomatic deteriorations (i.e. symptomatic progressions, which are not radiographically confirmed) will not be considered as progressions.

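### The SAP's PFS censoring note excludes progressions without radiographic confirmation, although the primary endpoint uses RANO progression, which includes clinical deterioration; the likely net effect is an upward shift in PFS-6 of unknown size

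*SAP*

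**What the plan says.** SAP 3.1.2 defines PFS-6 as the proportion of patients "who have survived without objective disease progression per RANO criteria for at least 6 months after enrollment", and SAP 8.2.2.2 repeats this. The estimate is Kaplan-Meier at 6 months with an "80% CI using the normal approximation to the log transformed cumulative hazard rate". SAP 4.1 states that nothing is tested.

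Protocol 9.3 and SAP 10.1 (Table 2) define progressive disease by any one of six items. One is "Clear clinical deterioration not attributable to other causes apart from the tumor"; another is "Failure to return for evaluation due to death or deteriorating condition". The summary tables in Protocol 9.4 and SAP 10.1 also mark worsening clinical status as sufficient alone.

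SAP 10.2, Table 4, Note (1), reads: "Symptomatic deteriorations (i.e. symptomatic progressions, which are not radiographically confirmed) will not be considered as progressions". Under Table 4, a patient with no counted event is censored at the last adequate scan or first dose, whichever is later. A death counts only within two scan intervals of the last adequate scan. New anticancer therapy before a counted progression also leads to censoring. SAP 10.1 leaves PFS sensitivity analyses optional and names none.

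**The concern.** The same patient can be a progressor under SAP Table 2 and be censored under Note (1). Protocol 5.7 lists documented clinical progression as a reason for removal from the study. Protocol 5.6 requires no study visits after the End of Study visit, and its tumor measurement at that visit is only if applicable. Later progression data come from "Passive follow-up only of radiologic imaging obtained subsequent to all on-study MRI scans and clinic visit notes". Some clinical-only progressions can therefore go without a confirming scan.

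These patients leave the risk set because they have just worsened, so the censoring is informative. With no hypothesis test, the PFS-6 estimate and its 80% interval are the efficacy result that will be read. The plan neither limits nor reports the number of patients affected.

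**Working it through.** **1. The plan's own figure.** The SAP (4.2.2) sizes each arm at 30 with a projected PFS-6 of 20%, that is 6/30. The exact two-sided 80% interval is Beta(0.10; 6, 25) = 10.86% to Beta(0.90; 7, 24) = 32.47%. The stated lower bound above 10% reproduces, and this concern does not affect it.

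The planned analysis uses the log-transformed cumulative hazard. With no censoring, SE = sqrt[(1 - S)/(nS)] / |ln S| = sqrt[0.8/(30 x 0.2)] / 1.609 = 0.227. The limits are 0.2^exp(±1.2816 x 0.227) = 11.6% and 30.0%.

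**2. One unrecovered progression before 6 months.** Take 30 patients, 24 progressing before 6 months and no other censoring. If one of the 24 is instead censored when n are at risk, KM = (n/30) x 6/(n - 1) = 20% x n/(n - 1).

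| n at risk | KM PFS-6 |
|---|---|
| 30 | 20.7% |
| 18 | 21.2% |
| 11 | 22.0% |
| 7 | 23.3% |

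Over 4,000 random draws on the Arm B scan schedule, one, two and three such patients give 21.1%, 22.3% and 23.6% on average. The mean interval for one patient is 12.3-31.5%. On the Arm A schedule the averages are 21.1%, 22.2% and 23.5%.

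**3. The opposite effect.** A clinical progression after 6 months whose last scan was before 6 months is moved to earlier censoring, which lowers KM. Suppose 7 are at risk at day 168 and one event follows before 6 months. Censoring one of the six later progressors at day 168 gives 7/30 x 5/6 = 19.4%.

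**4. Both effects together.** Large-sample simulation with 400,000 patients per run. From the documents: 8-week scans, the two-scan-interval (112-day) window and the projected 20%. Assumed: exponential PFS, the clinical-only share, a median of 1-4 months from clinical progression to death, and the probability that deterioration prompts a scan, taken 14 days later. The Arm A first scan is set at day 84.5 (7 + 21.5 + 56, midpoints). The comparator counts clinical progression as an event at its own date; radiographic progression is dated at the next scan in both versions. New therapy started before a scan was not modelled separately.

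Rise in KM PFS-6, percentage points:

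| Recovery of clinical-only events | Share 10% | Share 20% | Share 30% |
|---|---|---|---|
| Arm B, deaths only | 1.0-2.2 | 2.0-4.6 | 2.9-7.2 |
| Arm B, 50% scanned | 0.6-1.2 | 1.2-2.5 | 1.8-3.7 |
| Arm B, 80% scanned | 0.4-0.6 | 0.8-1.3 | 1.1-1.9 |
| Arm B, all scanned | 0.2-0.3 | 0.5 | 0.7-0.8 |
| Arm B, no recovery (upper limit) | 3.2 | 6.8 | 11.1 |
| Arm A, deaths only | 1.2-2.6 | 2.3-5.4 | 3.4-8.3 |
| Arm A, 80% scanned | 0.4-0.7 | 0.8-1.4 | 1.2-2.1 |
| Arm A, no recovery (upper limit) | 3.8 | 8.0 | 12.7 |

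**5. Table 5, separately.** Table 4 censors a progression found more than two scan intervals (2 x 56 = 112 days) after the previous adequate assessment. Table 5, row 3, gives 2 weeks (14 days). Scheduled scans are 56 days apart with ±7 days each (Protocol Appendices A and B), so 56 - 14 = 42 to 56 + 14 = 70 days apart. All these gaps are under 112 days and over 14.

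**The case against.** **The word objective.** The endpoint says objective progression, and the protocol elsewhere names radiologic and clinical progression separately (4.6, 5.5, 5.7). Note (1) could therefore be a deliberate imaging-only definition. That is a fair reading, and such an endpoint would be legitimate if labelled. But the follow-up table in Protocol 5.6 dates objective progression from the day RANO criteria for PD are met, and its footnote names clinic notes on neurologic state as a source alongside imaging. The texts conflict, and neither endpoint definition says imaging only.

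**Most cases may be recovered.** Protocol 5.5 has disease "assessed at eight-week intervals until objective disease progression, or as clinically indicated". SAP 2.1 agrees: "Tumor assessments will be performed every two cycles (eight weeks), or as otherwise clinically indicated". Both schedules also mark a tumor assessment at the End of Study visit. This stands: if deterioration usually prompts a scan, the effect is about 2 points or less, small beside an interval of 11.6-30.0%.

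**Clinical progression is hard to adjudicate.** It is judged by the investigator in an open-label trial. Clinical status is assessed by ECOG score, but no threshold for clear deterioration is given. The documents do not show whether the CRF holds a dated clinical RANO progression. This also stands, and is a reason to report both versions.

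**Two stronger readings to avoid.** A reader might infer that this censoring can never lower the KM estimate; the 19.4% example shows otherwise. A reader might also infer that Table 5, row 3, read literally, censors every progression on an on-schedule scan. Its wording counts from the last adequate post-baseline assessment, and Note (3) counts a scan showing PD as adequate, so on that reading the gap is zero. The wider censoring follows only if the 2 weeks run from the previous adequate assessment, as in Table 4.

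**Conclusion.** The concern holds as a conflict of definitions that should be fixed. Note (1) is narrower than the RANO definition the primary endpoint invokes, and it causes informative censoring of clinical-only progressions that are not recovered. The net effect on PFS-6 was upward in every scenario modelled.

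Confidence is high for the mismatch and low for the size, because the share, the recovery rate and the survival times are all assumptions. The documents do not support a claim that PFS-6 will be materially inflated: the effect could be a fraction of a point or several points. The 2-week entry in Table 5 is a separate reconciliation item and adds no weight to this conclusion.

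**What to change.** 1. Reconcile Note (1) with SAP Table 2 and with SAP 3.1.2 and 8.2.2.2. Either count any investigator-recorded RANO progression as an event at its documented date, including when it precedes new therapy, or state in the endpoint that only radiographic progression counts.
2. Whichever version is primary, prespecify the other as a PFS-6 sensitivity analysis in place of the optional wording in SAP 10.1. Report by arm the number of clinical-only progressions that were censored.
3. Separately, change Table 5, row 3, from more than 2 weeks to more than two scan intervals, counted from the same reference point as Table 4.

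The cost is wording, one sensitivity table and one correction. SAP 8.1.1 says follow-up has been terminated, so only progression already recorded can be used. Attribution to tumor may need review of clinic notes, and the full-RANO estimate may be slightly less favourable.

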(2) If target, non-target and new lesion assessments have different dates within a visit, then the earliest of those dates will be considered as the date of the tumor assessment if the assessment for that visit is progressive disease (PD); otherwise the latest date will be used.

(3) Adequate radiographical tumor assessment refers to an assessment with overall response of CR, PR, SD or PD.

(4) Comparing date of last tumor assessment to date of first dose is necessary if the last tumor assessment is baseline assessment

Table 5 PFS Censoring Reasons and Hierarchy

Hierarchy	Condition	Censoring Reason
1	No adequate baseline assessment	No adequate baseline assessment
2	Start of new anti-cancer therapy before event.	Start of new anti-cancer therapy
3	Event more than 2 weeks from last adequate post-baseline tumor assessment/start date	Event after missing assessments ^a
4	No event and [withdrawal of consent date \geq start date OR End of study (EOS) = Subject refused further FU]	Withdrawal of consent
5	No event and lost to follow-up in any disposition page	Lost to follow-up

6	No event and [EOS present OR disposition page for any EPOCH after screening says patient will not continue into any subsequent phase of the study] and no adequate post-baseline tumor assessment	No adequate post-baseline tumor assessment
7	No event and none of the conditions in the prior hierarchy are met	Ongoing without an event

For OS, patients last known to be alive are censored at date of last contact.

Date of Last Contact

The date of last contact will be derived for patients not known to have died at the analysis data cutoff date using the latest complete date (non-imputed) among the following:

- All patient assessment dates (e.g., blood draws [laboratory, PK], vital signs, performance status, ECG, tumor assessments, concomitant radiation, surgery)
- Start and end dates of follow-up anti-cancer therapies
- AE start and end dates
- Last date of contact where “Subject Remains in Follow-up” collected on the “Survival Follow-up” eCRF (do not use date of survival follow-up assessment unless status is alive)
- Study drug start and end dates
- Date of discontinuation on disposition eCRF pages (do not use if reason for discontinuation is lost to follow-up or death).

Note:

1. This list is not all inclusive and should be agreed upon by the study team according to the data collected in the CRF

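### SAP 10.2 gives two limits for the same PFS censoring level, 2 weeks in Table 5 and 2 scan intervals in Table 4, and does not say which governs

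*SAP*

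**What the plan says.** SAP 8.2.2.2, which defines the primary PFS-6 analysis, leaves censoring to the appendix: "The censoring rules for PFS will be detailed in 10.2". It does not name a table.

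Section 10.2 contains two tables. Table 4 assigns a date and an event or censored status to each situation. At level 3 it censors this case: "Tumor progression (per RANO) documented after 2 scan intervals following previous adequate radiological tumor assessment". Its last row makes the complementary case an event: "Tumor progression (per RANO) documented within 2 scan intervals following previous adequate radiological tumor assessment". Deaths have their own rows, and this one is an event: "No tumor progression (per RANO) but death reported within 2 scan intervals following last adequate radiological tumor assessment".

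Table 5 lists the same hierarchy with a condition and a reason for each level. Its level 3 condition is "Event more than 2 weeks from last adequate post-baseline tumor assessment/start date", and the reason given is that the event came after missed assessments.

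The lead-in describes the tables as follows: "Table 4 summarizes the censoring rules for the PFS analysis and displays censoring hierarchy for this study"; and then "Table 5 shows the general reasons for PFS censoring and where the censoring hierarchy in" Table 4 came from.

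**The concern.** The two tables give different limits for one rule. Two weeks is shorter than any gap between scheduled scans, so the Table 5 condition cannot pick out the missed assessments that its own reason column refers to. If it were programmed, with the gap measured from the previous scan, patients who attended every scan and progressed would be censored. Their progression would then drop out of the Kaplan-Meier estimate, and PFS-6 would be inflated. Median PFS, a secondary endpoint, uses the same derived variable.

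**Working it through.** **Inputs.**
- Scans are every 8 weeks (56 days) from the start of combination therapy (SAP 2.1; Protocol 5.5), with a window of ±7 days (Protocol Appendices A and B).
- Arm A has a run-in of 7 ± 2 days, then starts combination therapy 15 to 28 days after surgery (SAP 2.1). Its post-operative MRI is at 48 to 72 hours.
- PFS is counted from the first dose of any study drug (SAP 8.2.2.2).

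**Limits.** Table 4: 2 × 56 = 112 days. Table 5: 2 × 7 = 14 days. The ratio is 8.

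**Gap between a progression scan and the previous scan or start date.**

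| Situation | Gap in days | Table 4 | Table 5 |
|---|---|---|---|
| Consecutive scans, none missed | 56 − 14 = 42 to 56 + 14 = 70 | event | censored |
| First combination scan, Arm B, from first dose | 56 − 7 = 49 to 56 + 7 = 63 | event | censored |
| First combination scan, Arm A, from first dose | 5 + 15 + 49 = 69 to 9 + 28 + 63 = 100 | event | censored |
| Same, from the post-operative MRI | 15 − 3 + 49 = 61 to 28 − 2 + 63 = 89 | event | censored |
| One scan missed | 112 − 14 = 98 to 112 + 14 = 126 | event to 112, censored above | censored |
| Two scans missed | 168 − 14 = 154 to 168 + 14 = 182 | censored | censored |

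The tables disagree in every case without a missed scan and in part of the one-missed-scan case. They also differ in scope. Table 5 level 3 covers any event, so a death 15 to 112 days after the last scan is censored there but is an event under Table 4.

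**Another reading of Table 5.** Table 4, Note 3, says: "Adequate radiographical tumor assessment refers to an assessment with overall response of CR, PR, SD or PD". A scan showing progression is therefore itself adequate. Taken literally, the last adequate assessment is then the progression scan, the gap is 0, and level 3 would censor no progression at all. The comparison above takes the gap from the previous scan, as Table 4 does.

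**Planning figure.** SAP 4.2.2 projects PFS-6 of 20% with 30 patients per arm. The exact two-sided 80% interval for 6/30 is 10.86% to 32.47%, so the stated lower bound above 10% reproduces. It does not depend on the censoring limit. I used the 20% as the true value below.

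**Illustration of size.** Assumptions not in the documents: exponential PFS with S(182.6 days) = 0.20; 10 to 30% of first events are deaths; each scheduled scan is missed with probability 0 to 20%. An event is kept if its gap from the previous attended scan (or first dose) is within the limit, and otherwise censored at that point. There were 200,000 simulated patients per setting. Kaplan-Meier PFS-6:

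| Progressions found | 14 days, Arm B | 14 days, Arm A | 112 days, Arm B | 112 days, Arm A |
|---|---|---|---|---|
| All at scheduled scans | 0.812–0.936 | 0.840–0.945 | 0.219–0.259 | 0.263–0.327 |
| Half off schedule | 0.646–0.710 | 0.699–0.743 | 0.210–0.228 | 0.231–0.259 |

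In the first row the 14-day limit keeps 2.6 to 9.0% of events in Arm B and 2.3 to 7.8% in Arm A; the 112-day limit keeps 83 to 100% and 79 to 100%. Over the widest range tried (deaths 0 to 30%, off-schedule progressions 0 to 100%, missed scans 0 to 20%), PFS-6 is 0.520 to 1.000 with 14 days and 0.198 to 0.342 with 112 days. The excess over 0.20 under the 112-day limit comes from late detection at scans and censoring after missed scans, not from Table 5.

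**Hand check, Arm B, no scan missed.** The rate is −ln(0.20)/182.6 = 0.00881 per day. Under the 14-day limit only deaths within 14 days of a scan survive as events. Their share of deaths in a 56-day interval is (1 − e^(−0.00881×14))/(1 − e^(−0.00881×56)) = 0.116/0.390 = 0.30. With 10 to 30% deaths that keeps about 3 to 9% of all events, in line with the simulation.

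**The case against.** The best reply is that the intended rule can be recovered from the same pages. Table 4 is introduced as the rules for this study, and it alone assigns dates and event status. Two scan intervals appears in six of its situations, against one mention of two weeks. The Table 5 reason concerns missed assessments, and SAP 8.2.3.1 defines the PFS event as documented progression or death. A programmer who censored nearly every progression in patients with complete scans would probably notice. The text of footnote a, attached to this row, is not visible in the supplied document and might clarify it. No PFS summary is produced at all for an arm with fewer than 10 patients.

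Most of this stands. It supports reading two weeks as a slip and treating the simulated values as conditional. It does not settle precedence: the lead-in also calls Table 5 the origin of the hierarchy, and SAP 7.4 and 8.2.2.2 point to 10.2 as a whole. Table 5's conditions are written in terms of disposition pages and end-of-study status, which makes it a natural source for code. The missing footnote is not counted against the plan. The 10-patient minimum limits when the effect could arise but leaves the contradiction in place.

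**Conclusion.** The concern holds. SAP 10.2 states two incompatible limits, 14 and 112 days, for the same PFS censoring level, and every gap without a missed scan (42 to 100 days across arms and starting points) falls between them. That part follows from the documents alone, given the gap is measured from the previous scan and two scan intervals means 2 × 8 weeks, since the SAP gives no figure in days. Table 4 as written does not bias PFS-6 in this way. The inflation to roughly 0.65 to 0.95, against 0.21 to 0.33, arises only if Table 5's limit is programmed, and rests on the assumed event distribution, death share, missed-scan rate and off-schedule share (none or half). The intent is recoverable, but this is a wrong threshold in a stated rule for the primary analysis and should be corrected.

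**What to change.** In Table 5, level 3, replace the 2-week limit with 2 scan intervals, measured from the previous adequate assessment before the event, or from the start date if there is none. This also removes the zero-gap reading under Note 3. Add one sentence to 10.2: Table 4 determines event or censoring status and date, for progressions and deaths alike, and Table 5 supplies only the reason label.

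In the same edit it would help to give two scan intervals in days and say whether the ±7-day windows are added, because gaps after one missed scan (98 to 126 days) straddle 112.

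The cost is one table cell and one sentence, plus the optional definition in days. No new data are needed.
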